#### Step 1: Identification of Potential Participants

- Participants will be identified in a variety of ways and will be *tailored* based on the recruitment site. Patients identified through a clinical site (ABC, IUH) will be identified via the Indiana Network for Patient Care, which can access patient lists by doctors and clinic and PC clinic schedules. To identify potential participants at BIDMC, a data manager at BIDMC will send a research assistant a list of all women 75-89 years with dementia (based on ICD-10 codes [will be expansive and will include codes for memory loss and all forms of dementia]) and without a history of breast cancer scheduled to see their primary care provider (PCP, physician or nurse practitioner). With a HIPAA waiver a research assistant (RA) will then review these patients' medical records to see if the patient meets eligibility criteria (e.g., diagnosis of Alzheimer's or related dementia; mammogram in the past 5 years but not in the past 6 months, no history of breast cancer listed in problem list). Patients' physicians will be notified first of their patient's potential eligibility and be asked if DECAD can approach the patient and their caregiver for participation. Physicians are routinely given 2 weeks to review their patient list (per IU PBRN). At BIDMC, physicians are routinely given 2 days to respond to an email requesting permission to contact their patients. However, if the physician has an out-of-office response we give PCPs 2 days to respond after they return. The email informing PCPs that we plan to contact their patients tells PCPs that if we do not hear from them in 2 days then we will send their patients an informational letter about the study. Once approved by physician, the patient and caregiver will get a letter informing them of the study and that study personnel will be calling them in 1-2 weeks to provide more information. Participants identified from non-clinical sites (eg. Alz Assoc) will receive information about the study from the Alz Asso and from Trial Match. They will reach out to the study team directly or will provide permission to be follow-up by the study team regarding recruitment. We will also present the study at community events such as caregiver support groups and Alzheimer's related events. Caregivers approached at these events will have the opportunity to sign a contact list that includes their phone number, to hear more information about our study. The study team will then reach out to those caregivers to assess eligibility and confirm interest in participation. We will use our pre-approved brochure for these caregivers.
- We will consider any woman age  $\geq 75$  years with a diagnosis of AD or related dementia who has received a mammogram in the past 5 years (but not in the past 6 months) and who does not have a history of breast cancer or documentation in her EMR that she has decided to stop mammography.
- We will approach the primary family caregiver/ informant for each eligible woman. Caregivers will be eligible if they are a caregiver for the patient and intend to accompany the patient to their next primary care visit.
- Rolling enrollment will take place over 36 months with an average monthly enrollment of 11-12 dyads.

Figure 1.

DECAD ↵

# DECAD Study Timeline

## Step 2: Enrollment

- Following eligibility determination and the informed consent process (which includes HIPAA release form), and baseline assessment the dyads will be randomly assigned in 1:1 ratio to one of two groups: mammogram decision aid or home safety guide, stratified by site.
- Decision aid or home safety guide will be mailed to both the patient and the caregiver immediately after randomization but at least 1 week before the index visit.
- Date of the patient's next PCP visit will be obtained via caregiver report at the baseline interview and via EMR review at the time of enrollment.
- For all dyads, the Research Assistant will meet them in person or by phone 0-2 days before the index visit to standardize the process by which all dyads review the decision aid. The pre-index visit assessment (T2) will occur in-person or by phone 30 minutes-2 days before the index visit either at the patient's house, at the caregiver's house, at the provider office or at a location of the dyads choice. Observational data only is collected at this assessment. The RAs will not discuss the content of the decision aid at that time; they will simply ensure that they have read it or have had it read to them before the index visit. We will record if the RA is asked to read the DA to either member of the dyad. If

the dyad has any questions about the content of the decision aid, the RA will encourage them to ask the patient's provider any questions. The phone option script will provide prompts to ensure review of the decision aid during the phone conversation

- If the date of the patient's index visit is not known or not documented in the EMR, the RA will follow the study tracking process to obtain the patient's index visit appointment date. This includes a 2x per month phone call to the caregiver and EMR review (if accessible).
- If the index PCP visit does not occur within approximately six months of the baseline, another provider visit may be substituted with PI permission.
- The post- index visit (T3) will occur in-person or via phone 0-5 days after the index visit.
- The 15 month follow-up (T4) will be in-person or via phone and include an assessment with the caregiver and a review of the patient's EMR. This interview may be audio recorded. In the event we have exhausted the attempts to reach the participant/caregiver by phone or in person, we will send a paper copy of a letter explaining the request to have them complete the survey on paper and return to the research assistant.
- The 24 month follow-up (T5) will include a review of the patient's EMR (only).
- See Table 3 and Figure 1 for a complete list of measures and timing of collection.

*Statistical Plan:*

Step 1: Overview

- For analysis, we will examine univariate distributions of continuous variables in order to detect any potential violations of assumptions to our planned parametric methods of analyses.
- We will transform variables as needed to ensure normal distribution assumptions are met.
- We will use nonparametric methods if transformations are inadequate.
- Demographic characteristics of the patients and caregivers will be compared between the two groups in order to evaluate if randomization is effectively balanced. We will include caregiver sex as a moderating biological variable and examine the influence of sex on caregivers' decisional conflict and other factors associated with the impact of our decision aid interaction on mammography screening use.
- We will use Chi-squared tests or Fisher's exact tests to compare the frequencies of categorical variables. Analysis of variance (ANOVA), or its nonparametric alternative, the Wilcoxon rank sum test, will be used to compare the distribution of continuous variables between the groups.
- We will use SAS 9.4 for all analyses (SAS Institute, Carey, NC).

Step 2: Primary Aim

- Analysis of covariance (ANCOVA) models will be used to compare mean Decisional Conflict Scale (DCS) scores between the intervention and control groups. For each caregiver, the difference in DCS scores from baseline to follow-up will be used as the dependent variable in the ANCOVA with randomization group assignment as the independent variable adjusting for the stratification variable of recruitment site and for other potential baseline covariates that are found to be significantly different between the two groups in univariate comparisons.

- ANCOVA models will also be used to compare secondary decision quality outcome (e.g., decision-making self-efficacy) at follow-up between the intervention and control groups adjusting for site and other potential baseline covariates found to be significantly different between the two groups in univariate comparisons.

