Primary outcome	Feel Informed Values clarification	Decisional Conflict	Decision Conflict Scale	16-items on a 1-5 Likert scale. Measures uncertainty around a decision, whether	Scores range 0-100; Lower	T1 T3	Caregiver reported

				one feels informed, clear about their personal values, and supported in their decision-making.	scores indicate less conflict.		
Secondary outcomes	Belief in ability to make and participate in shared decision making	Decision-making self-efficacy	Decision Self-Efficacy Scale (DSE)	11-items on a 5-point Likert scale. Measures of self-confidence or belief in one's ability to make decisions	Low, medium, high decision self-efficacy. Scores range 0-100	T1 T3	Caregiver reported
		Receipt of screening	DECAD Created	Review primary care notes, radiology reports, and documentation on screening/preventive care; caregiver report	Yes or no determination	T4 T5	Pt EMR; Caregiver reported
	Involvement in the decision	Caregiver role in decision-making	Adapted from the Control Preferences Scale	4-items to assess preferences for and involvement in making decisions on their own or sharing responsibility with the pt or doctor.	Active vs. passive/shared with doctor (since aim of decision aids is to help dyads be more active in decision-making)	T3	Caregiver reported
		Patient role in decision-making	Adapted from the Control Preferences Scale	2-items to assess involvement in making decisions on their own or sharing responsibility with their family or doctor.	Active vs. passive/shared with doctor (since aim of decision aids is to help dyads be more active in decision-making)	T3	Patient reported
Other measures		Socio-demographics	DECAD Created	32 item questionnaire to measure items such as relationship to the patient, frequency and type of contact with the patient, geographic distance from the patient, education level, annual income, self-reported health status, etc.	Co-variates	T1	Caregiver reported
	Does severity of the patient's cog and functional impairment impact caregiver decision making	Severity of patient's cognitive impairment	Dementia Severity Rating Scale (DSRS)	12-item questionnaire for caregivers to assess severity of AD in 12 major functional and cognitive domains.	Score ranges from 0 (mild) to 54 (severe).	T1	Caregiver reported
			Caregiver Appraisal of Function and Upset (CAFU)	15-item questionnaire for caregivers to measure ADLs and iADLs impairment and how much those impairments upset or burden the caregiver		T1	Caregiver reported

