#### Step 3: Secondary Aim

- A binary indicator variable for receipt of mammograms within 15 months and within 24 months from the intervention date will be used as a secondary outcome variable.
- A logistic model with group (decision aid or control) as the independent variable will be used adjusting for recruitment sites (e.g., EH, IUH and IADC) and other potential baseline covariates found to be different in univariate comparisons.

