## **STATISTICAL POWER**

Sample size for the proposed trial is calculated using our pilot data that showed effect sizes of 0.28 on Decision Conflict Scale (DCS) score and 0.34 for self-efficacy scores. To detect effect size of 0.28 or greater on DCS scores between the two groups, we will need to have 202 patient/caregiver dyads per group to complete both baseline and follow-up with 80.2% power using two sample *t*-test at 0.05 level. Allowing 5% missing data at follow-up, we will need to enroll 213 patient/caregiver dyads per group (total 426 dyad baselines). With our planned sample size, we will have 92.6% to detect effect size of 0.34 or greater on changes in self-efficacy scores between the two groups.

The pilot showed the mean DCS were similar between the two groups, the control group had a large SD which should come down with large sample size. Table 4.

Table 4. Baseline DCS scores						
Group	N	Mean	Std Dev	Std Err	Minimum	Maximum
Control	8	26.8375	22.6769	8.0175	0	69.0000
Decision support	9	26.4444	16.4249	5.4750	0	45.0000

Change in DCS from baseline to follow-up: DA group had greater decrease in DCS than controls. The current effect size is about 0.55. Table 5.

Table 5. Change in DCS scores from baseline to follow-up, by group						
Group	N	Mean	Std Dev	Std Err	Minimum	Maximum
Control	8	5.2000	8.8073	3.1139	-6.0000	21.0000
Decision support	9	9.7778	7.8705	2.6235	0	20.0000
Diff (1-2)		-4.5778	8.3208	4.0432		

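### Neither the decisional conflict model nor the self-efficacy model fixes its own baseline score as a covariate, and both choose other covariates by chance differences between the arms

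*Combined protocol and SAP*

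**What the plan says.** All references are to the combined protocol and SAP.

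- **Primary model (Statistical Plan, Step 2: Primary Aim).** For each caregiver, "the difference in DCS scores from baseline to follow-up will be used as the dependent variable in the ANCOVA". Group is the independent variable and recruitment site is adjusted for. The remaining terms are "other potential baseline covariates that are found to be significantly different between the two groups in univariate comparisons".
- **Screening (Step 1: Overview).** "Demographic characteristics of the patients and caregivers will be compared between the two groups", to see whether randomisation achieved balance. There is no list of candidate covariates and no significance threshold.
- **Self-efficacy model (Step 2).** ANCOVA is used to compare the "secondary decision quality outcome (e.g., decision-making self-efficacy) at follow-up between the intervention and control groups adjusting for site", with the same selection rule for further covariates.
- **Mammogram receipt (Step 3: Secondary Aim).** The logistic model adjusts for site and "other potential baseline covariates found to be different in univariate comparisons".
- **Missing data (Step 5).** Variables that differ significantly between completers and non-completers are also added to the ANCOVA models.
- **Measurement (Table 3).** DCS and self-efficacy are both collected at T1 and T3, so both baseline scores will be available.
- **Power (Statistical Power).** An effect size of 0.28 on DCS with 202 completers per group gives 80.2% power by a two-sample t-test. For self-efficacy, "we will have 92.6% to detect effect size of 0.34 or greater on changes in self-efficacy scores between the two groups". The same section first gives 0.34 for self-efficacy scores, without calling them changes.

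**The concern.** The baseline value of an outcome is usually its strongest predictor. Here neither model names it, and calling the model ANCOVA does not supply it, because the listed adjustment terms leave it out.

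The selection rule does not repair this. Allocation is randomised, so any baseline difference is a chance one. A baseline score would pass a 0.05 imbalance test only about 5% of the time, whatever its prognostic value. The rule also leaves the primary model unfixed until the arms have been compared. With no candidate list and no threshold, two analysts following the plan could fit different models.

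The two outcomes differ in what is lost. A change score uses baseline DCS, but with the slope fixed at 1, which over-corrects a chance imbalance when the true slope is lower. The self-efficacy model ignores the baseline entirely, and its power is quoted for a different quantity from the one it analyses.

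**Working it through.** **Inputs.** 202 completers per arm, effect sizes 0.28 and 0.34, 0.05 level (Statistical Power). Pilot SDs come from Tables 4 and 5. The T1–T3 correlation ρ is not given, so a range is shown. T1 and T3 SDs are assumed equal. Power uses the noncentral t distribution, two-sided.

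**Plan's own figures.** Effect 0.28 gives 80.2%, and 0.34 gives 92.6%. Both reproduce. 202/0.95 = 212.6, so 213 per arm also reproduces.

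**Pilot-implied ρ for DCS.** The pooled baseline SD is √[(7×22.6769² + 8×16.4249²)/15] = 19.592. The pooled change SD is 8.3208. Then ρ = 1 − 8.3208²/(2×19.592²) = 0.91, from 17 dyads.

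**DCS with baseline always included.** Taking 0.28 in change-SD units, the variance ratio to the plain change score is (1+ρ)/2, so the effective size is 0.28×√(2/(1+ρ)).

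| ρ | Effective size | Power | Reduction in SE |
|---|---|---|---|
| as planned | 0.280 | 80.2% | – |
| 0.91 | 0.287 | 81.9% | 2.3% |
| 0.7 | 0.304 | 86.1% | 7.8% |
| 0.5 | 0.323 | 90.0% | 13.4% |

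**Over-correction by the change score.** In change-SD units the shift is imbalance × √((1−ρ)/2). One SE of imbalance is √(2/202) = 0.0995 SD, and the p = 0.05 boundary is 0.196 SD. At ρ = 0.91, 0.7 and 0.5:

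- a 1-SE imbalance moves the estimate by 7.5%, 14% and 18% of the 0.28 target;
- a boundary imbalance moves it by 15%, 27% and 35%.

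These shifts average zero over randomisations.

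**The rule by simulation.** 6,000 trials per setting, with baseline DCS entering only if the arms differ at p < 0.05 and no other covariates.

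| ρ | Power, rule | Power, always included | Type I error, rule |
|---|---|---|---|
| 0.5 | 82.0% | 90.6% | 4.2% |
| 0.7 | 81.5% | 86.0% | 4.7% |
| 0.9 | 79.8% | 81.4% | 5.0% |

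The rule recovers almost none of the available precision, and it does not inflate type I error.

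**Self-efficacy, 0.34 in change-SD units.** Follow-up score alone has effective size 0.34×√(2(1−ρ)). With baseline included it is 0.34×√(2/(1+ρ)).

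| ρ | Follow-up only: size, power | With baseline: size, power |
|---|---|---|
| 0.3 | 0.402, 98.1% | 0.422, 98.8% |
| 0.4 | 0.372, 96.2% | 0.406, 98.3% |
| 0.5 | 0.340, 92.6% | 0.393, 97.6% |
| 0.7 | 0.263, 75.2% | 0.369, 95.9% |
| 0.9 | 0.152, 33.2% | 0.349, 93.8% |

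If 0.34 is instead in follow-up-SD units, the planned model has 92.6% at any ρ. Baseline adjustment then gives size 0.34/√(1−ρ²), which is 97.6% power at ρ = 0.5 and more above that.

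**Chance selection.** Assuming a 0.05 threshold and independent variables, screening 10 gives 1 − 0.95¹⁰ = 40% probability that at least one enters. Table 3 lists a "32 item questionnaire to measure items such as relationship to the patient" and other features. Screening all 32 items, as an upper illustration, gives 1 − 0.95³² = 81%, with 32×0.05 = 1.6 expected to enter.

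**The case against.** The strongest reply is that the primary analysis contains no error. The test is valid, the stated power is reached, and a change score already uses the baseline. At the only correlation the documents support, 0.91, adding baseline DCS gains 1.7 points of power. This stands as a limit on size. That correlation rests on 17 dyads and equal SDs, however, so a small gain cannot be counted on.

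The effect scale is also unsettled. The pilot change data give 4.5778/8.3208 = 0.55 ("The current effect size is about 0.55"). The 0.28 may be on the raw-score scale, since 4.5778/16.4249 = 0.279, though the plan does not say so. On that reading the planned model has 95.2% power against 97.6% adjusted at ρ = 0.7, both exceed 99.9% at 0.91, and the full 10-point gain remains only at 0.5. If 0.55 is the true change effect, power exceeds 99.9% either way. These points stand.

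For self-efficacy there is no documented correlation, the outcome is secondary, and it does not set the sample size. Below ρ = 0.5 the planned model exceeds its stated power. That is correct, but the mismatch between the model and the power statement remains at any ρ.

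Three smaller points hold in part. The imbalance shifts are already reflected in the SE loss and are not a separate harm. The sociodemographic items are unlikely to be independent, so 40% and 81% are only illustrations. Step 1 names demographics, but Step 2 speaks of baseline covariates generally, so baseline DCS may well be screened. Being screened would still bring it in only about one time in twenty.

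**Conclusion.** The concern holds and should be fixed. It is a matter of efficiency and prespecification, not validity: type I error is not inflated, and 80.2% power is met with 0.28 on the change scale.

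For DCS, the plan forgoes between about 2 and 10 points of power for ρ from 0.91 down to 0.5, given equal SDs and 0.28 on the change scale. The power gain vanishes if the pilot effect of 0.55 is real, although the SE reduction of 2.3% to 13.4% does not depend on the effect size.

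For self-efficacy, the 92.6% need not apply to the planned analysis. If 0.34 is on the change scale, power falls short whenever ρ exceeds 0.5, to 75.2% at 0.7. If 0.34 is on the follow-up scale, 92.6% is right for the model but the power statement is worded for the wrong quantity. Including the baseline score gains precision on either reading.

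Whatever ρ is, the primary model is not fixed in advance.

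**What to change.** - In Step 2, specify baseline DCS and site in the primary model, and baseline self-efficacy and site in the self-efficacy model, fitted whatever the baseline p-values. With the baseline score included, change and follow-up scores give the same treatment estimate, so the choice of dependent variable no longer matters.
- Name any further prognostic covariates before unblinding.
- Delete selection by baseline difference from both Step 2 models and from Step 3.
- Restate the self-efficacy power on the scale of the model to be fitted, and say which scale 0.28 and 0.34 are on.
- Keep the Step 5 completer/non-completer adjustment as a labelled sensitivity analysis, separate from the primary model.

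No new data are needed, since both scores are collected at T1. The cost is one degree of freedom per model for the baseline score, and a few more if other covariates are named. The document is dated April 2022 and its timeline starts in October 2017, so T3 data may already exist. The change should therefore be dated and justified in the SAP before the arms are compared.

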#### Step 3: Secondary Aim

- A binary indicator variable for receipt of mammograms within 15 months and within 24 months from the intervention date will be used as a secondary outcome variable.
- A logistic model with group (decision aid or control) as the independent variable will be used adjusting for recruitment sites (e.g., EH, IUH and IADC) and other potential baseline covariates found to be different in univariate comparisons.

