**Primary Aim: To examine the effect of a mammography screening decision aid intervention for older women with AD on markers of decision quality among caregivers.**

Hypothesis: Caregivers of patients who receive the decision aid will have lower levels of decisional conflict (primary outcome) and higher levels of decision-making self-efficacy (secondary outcome) about breast cancer screening in older women with AD, compared to the control group.

**Secondary Aim: To examine the effect of a mammography screening decision aid intervention for caregivers on the utilization of mammograms in older women with AD.**

Hypothesis: Women with AD who are randomized to receive the decision aid will receive less mammography screening at 15 and 24 months after the intervention, compared to the control group.

**Exploratory Aim: To identify the factors that are associated with impact of a decision aid intervention on mammography screening cessation in older women with AD.**

Exploratory Hypothesis: Among the dyads randomized to receive the decision aid, caregivers of patients with more severe cognitive impairment, greater co-morbidities, or older age will experience a greater reduction in frequency of mammograms in the 15 and 24 months following the intervention.

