**Table 1. Inclusion and exclusion criteria for the DECAD Trial**

INCLUSION CRITERIA	
Patients	Caregivers
Female and 75 years or older	18 years or older
At least one mammogram in the past five years	Primary family caregiver of the patient*
Primary care visit scheduled in the next 12 months	
Diagnosis of AD as determined by ICD-10 code	Ability to provide informed consent
Ability to provide informed consent or assent	
Ability to communicate in English	Ability to communicate in English
EXCLUSION CRITERIA	
Patients	Caregivers
Permanent resident of a nursing facility	Caregiver is a non-family member who is not a legal Healthcare Power of Attorney
Had a mammogram in the past 6 months	Less than a 7 th grade education**
Primary care visit scheduled is not the first visit with the PCP	
Made a decision to stop getting mammograms	Made a decision that the patient will stop getting mammograms
History of Atypical Ductal Hyperplasia, lobular carcinoma in situ, ductal carcinoma in situ, or invasive breast cancer or other cancer in the past 5 years.	Has a diagnosis of AD or has a serious mental illness such as bipolar or schizophrenia as determined by ICD-10 code
Has mild cognitive impairment, serious mental illness such as bipolar or schizophrenia as determined by ICD-10 code	

\* Identified by the patient or listed as primary caregiver in EMR.

\*\*The reading level of the decision aid is 7th grade.

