**Table 2. Sites for DECAD Recruitment\***

Site	Number of sites	# of Physician s	Women ≥70 years old with AD	Race and Ethnicity for population with AD
Eskenazi Health Aging Brain Care Program	1	5	1,383	White 42% African American 51% Other or unknown 7% Hispanic 2%
Indiana University Alzheimer Disease Center	1	NA	43	White 67.5% African American 32.5%
Indiana University Health Department of Neurology	1	3	TBD	TBD
Alzheimer's Association- Greater Indiana Chapter	5-10	NA	TBD	TBD
IU Health PC		179	2,026	White 75.6% African American 22.4%

- Caregivers will be age 18 and older and an unpaid, informal caregiver for the patient either self-identified, identified by the patient, or identified by the patient's medical team.
- See Table 1 for patient and caregiver inclusion and exclusion criteria.

*Recruitment Sites (as of 11/30/2021):*

- Aging Brain Care Program at Eskenazi Health
- Indiana University Alzheimer Disease Center (research registry)
- Indiana University Health Department of Neurology
- Indiana University Health Department of Psychiatry (Drs. [name] and [name])
- Alzheimer's Association- Greater Indiana Chapter (Support Group members)
- Indiana University Health Primary Care Practices in central Indiana
- Eskenazi Health Primary Care Practices in central Indiana
- Beth Israel Deaconess Medical Center, Boston, Massachusetts
- Parkview Health, Fort Wayne, Indiana
- CICOA Aging and In-Home Services, central Indiana
- LifeStream Services, eastern Indiana
- Thrive Alliance, southern central Indiana
- SWIRCA & More, southwest Indiana

	14 PC practices			Other or unknown 2% Hispanic 0.9%
BIDMC	7 sites	90	1600	White- 64% Black- 23% Asian- 4% Hispanic -5%
Parkview Health	TBD	TBD	TBD	TBD
CICOA Aging and In-Home Services	NA	NA	988	TBD
LifeStream Services	NA	NA	200	TBD
Thrive Alliance	NA	NA	40	TBD
SWIRCA & More	NA	NA	90	TBD
Total	34	277	6280	

\*Data as of March 2017 besides BIDMC, Parkview Health, CICOA, LifeStream, Thrive Alliance, SWIRCA & More

*Primary outcome:* Caregiver decisional conflict at post-index visit (T3)

*Secondary outcome (caregiver):* Caregiver decision-making self-efficacy at post-index visit (T3)

*Secondary outcome (patient):* Utilization of mammograms at 15 (T4) and 24 months post-index visit (T5).

Table 3. Measures							
Outcomes	Construct/Core Attributes	Outcome measure(s)	Name of Measure citation	Description	Scoring	When	Source

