### *Intervention Description and Timing of Measures*

Although participants may be recruited from specialty memory care or AD clinics, the intervention will be delivered in the patient's primary care setting (e.g. the usual setting for discussions about mammography).

[figure not shown]

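### The mammogram outcome has no single defined time zero: the analysis counts from an undefined intervention date, the outcome list from the index visit.

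*Combined protocol and SAP*

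**What the plan says.** Three places describe when the mammogram outcome is counted.

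- Statistical Plan, Step 3 (Secondary Aim): a binary indicator for "receipt of mammograms within 15 months and within 24 months from the intervention date".
- Secondary outcome (patient), listed after Table 2: "Utilization of mammograms at 15 (T4) and 24 months post-index visit (T5".
- Secondary Aim hypothesis, Background and Study Aims: women given the aid "will receive less mammography screening at 15 and 24 months after the intervention, compared to the control group".

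The date of the intervention is not defined in any of them. Other passages offer several candidates. Under Step 2 (Enrollment), the aid or the home safety guide "will be mailed to both the patient and the caregiver immediately after randomization but at least 1 week before the index visit". The same section describes a contact with the research assistant 0-2 days before the index visit, to make sure the material has been read. The section on intervention and timing says that "the intervention will be delivered in the patient's primary care setting", which could point to the visit itself.

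Two passages bear on the time from mailing to visit. Table 1 requires "Primary care visit scheduled in the next 12 months". Step 2 adds: "If the index PCP visit does not occur within approximately six months of the baseline, another provider visit may be substituted with PI permission".

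**The concern.** Mammography use is the whole of the Secondary Aim, and it also feeds the Exploratory Aim. A yes/no outcome within a fixed window needs a fixed start. Here the start could be the mailing, the review contact or the index visit, and the choice matters in different ways.

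If the start is the mailing, Step 3 and the outcome list define two different windows. A mammogram between mailing and visit counts only under the mailing rule. A mammogram more than 15 (or 24) months after mailing, but within 15 (or 24) months of the visit, counts only under the index-visit rule. An analyst could choose between them after seeing the data.

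If the start is the index visit, the passages agree, but the clock begins at an event after randomisation. The aid is by then in the home, for at least a week and perhaps for months. Screening obtained or declined in that time is part of what the aid might change, yet it falls outside the outcome. Table 1 excludes women with a mammogram in the previous 6 months, so some enrolled women may fall due in that interval. A dyad whose visit never takes place has no window at all.

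**Working it through.** **The plan's own figures.** The Statistical Power section covers only the caregiver scales: 202 completers per group for 80.2% power at effect size 0.28. This reproduces (80.16% with the noncentral t, two-sided 0.05), and 202/0.95 = 212.6 gives the 213 per group. The documents give no mammogram rate, no distribution of the gap and no power for the mammogram outcome, so what follows is illustrative.

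**Inputs from the documents.** Window length W = 15 or 24 months. Minimum gap 1 week (7/30.4375 = 0.23 month). A gap of about 6 months is where another visit may be substituted; that limit runs from baseline, and randomisation follows the baseline assessment. I add 3 months as a middle value.

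**Assumptions, not in the documents.** A constant mammogram rate h, the same before and after the visit, with independent repeat mammograms. Receipt within 15 months is p = 40%, range 20-50%. The intervention date is the mailing date.

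**Overlap of the windows.** Shifting a window by g leaves g/W of each unshared. At 15 months that is 0.23/15 = 1.5%, 3/15 = 20% and 6/15 = 40%. At 24 months it is 1.0%, 12.5% and 25%.

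**Women classified differently.** With h = -ln(1-p)/15:

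- yes by mailing, no by index visit: a mammogram in the gap and none in the W months after the visit, (1 - exp(-hg)) × exp(-hW);
- no by mailing, yes by index visit: none in the W months after mailing and one in the following g months, which has the same probability.

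The total is 2 × (1 - exp(-hg)) × exp(-hW). At W = 15, exp(-hW) = 1 - p.

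For p = 0.40, h = 0.5108/15 = 0.0341 per month:

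| Gap | Any mammogram in gap | Differs, each end | Differs, total at 15 months | Range, p = 20-50% |
|---|---|---|---|---|
| 1 week | 0.8% | 0.5% | 0.9% | 0.5-1.1% |
| 3 months | 9.7% | 5.8% | 11.7% | 7.0-12.9% |
| 6 months | 18.5% | 11.1% | 22.2% | 13.7-24.2% |

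The 3-month row, for example, is 2 × 0.0971 × 0.60 = 0.117. If every one of the 426 dyads had that gap, this would be about 50 women (426 × 0.1165).

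At 24 months, exp(-hW) = 0.6^(24/15) = 0.442. The totals are 2 × 0.0971 × 0.442 = 8.6% for 3 months and 2 × 0.1848 × 0.442 = 16.3% for 6 months (ranges 6-9% and 12-16%).

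**Other readings of the date.** If it is the review contact, the shift is 0-2 days. If it is the index visit, the shift is zero and the table does not apply; what remains is the post-randomisation start.

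**Net effect.** Under a constant rate both rules give the same overall 40%, because the two ends cancel. The calculation therefore measures how many women change category. It does not measure a shift in the treatment effect.

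**The case against.** The strongest reply is that no contradiction is proved. The intervention is said to be delivered in primary care, the review contact takes place within two days of the visit, and T4 and T5 are labelled by the index visit. Read together, these suggest that the intervention date is the index visit, give or take two days. Figure 1, the study timeline, is not available here and may show the anchor. This much stands: the two-window problem is conditional on the mailing reading.

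The reply can go further. A scheduled visit is an entry criterion and its date is sought at the baseline interview, so time zero is often known before allocation. A substitute visit is allowed. A clock from the decision visit is also a legitimate choice of estimand. These points soften the concern but do not remove it. Step 2 provides for visits whose date is unknown, with repeated calls to the caregiver to find it. Substitution is discretionary. Step 5 expects missing mammogram data only from death or a move out of state, and so does not address a dyad without a visit.

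Two stronger inferences are tempting and are not supported. A reader might infer bias between the arms, but both arms are mailed material at the same point and follow the same visit schedule, and nothing in the documents shows that the gap differs by arm. A reader might also infer that women with no index visit are excluded from the analysis. The plan does not say so; it leaves them without a defined window, and their number is unknown.

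**Conclusion.** The concern holds in a conditional form and should be fixed. The intervention date is undefined, and each plausible reading leaves a defect: two windows for one endpoint if it is the mailing, or a post-randomisation start that ignores screening behaviour after exposure if it is at or close to the index visit.

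On the mailing reading, the size depends mainly on the gap. Reclassification at 15 months is negligible at the 1-week minimum and reaches roughly one woman in five at six months, with half of it at each end of the window. That rests on an assumed constant rate and an assumed 15-month receipt of 20-50%. The share of women with any mammogram in the gap (9.7% at 3 months, 18.5% at 6 months, for p = 40%) should not be read as the share reclassified, because many of them would also have a mammogram inside the other window.

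This is a poorly defined endpoint that loses events after exposure and leaves a choice to the analyst. It is not a demonstrated bias in the comparison of arms.

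**What to change.** Use one definition in the Secondary Aim hypothesis, the outcome list after Table 2, and Step 3 of the Statistical Plan, and settle it before mammogram data are examined by group. Suggested wording: *receipt (yes/no) of at least one screening mammogram within 15 months, and within 24 months, of the date of randomisation, for every randomised dyad in both arms.* Specifying screening matches the Table 3 entry on receipt of screening. Keep the index-visit clock as a named sensitivity analysis.

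Three practical points follow.

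- For dyads with an index visit, T4 and T5 are dated from that visit and so fall after the randomisation windows close. The planned record reviews can be abstracted back to randomisation.
- For dyads with no index visit, T4 and T5 have no date under the present wording. Date their record review from randomisation.
- Where the medical record is not accessible, word the T4 caregiver question to cover the whole period since randomisation.

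The cost is a few changed sentences and slightly more record abstraction. The downside is that the main window then includes some time before the decision visit; the sensitivity analysis shows how much that matters.
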